#### 8.8.4.8 *Explant*

Number and percentage of patients with an explantation will be tabulated. Time to first explantation relative to initial implant will be assessed using descriptive statistics (sample size (N), mean and 95% confidence intervals for the means, minimum, maximum, median, and standard deviation). Also the time to first explantation relative to initial implant in the following categories:

- Explant occurred  $\leq 30$  days after implant
- Explant occurred  $\leq 180$  days after implant

- Explant occurred > 180 days after implant

The number and percentage of patients who had their LVAD device replaced will be tabulated. The number and percentage of patients who received a new HeartWare MVAD® device will also be tabulated. The number and percentage for reasons for explanation will be tabulated. Since patients can have multiple explants, the reasons for explantation will include all reasons. Therefore the percentages may add up to more than 100%.

Time to first explantation will be presented graphically as a Kaplan-Meier curve. Any withdrawal or lost to follow-up will be censored at the time of this event date. For each patient that remains alive on device, time to first explantation will be censored at the time of last contact date known to be alive (contacts considered in the determination of last contact date would include but not limited to scheduled visit dates, adverse event dates, and last known alive date).

Time to first exchange will be presented graphically as a Kaplan-Meier curve. If a patient had transplant or explants for recovery, and any withdrawal or lost to follow-up will be censored at the time of this event date. For each patient that remains alive on device, time to first exchange will be censored at the time of last contact date known to be alive (contacts considered in the determination of last contact date would include but not limited to scheduled visit dates, adverse event dates, and last known alive date).

## **8.9 Pharmacodynamics**

Not applicable to this study.

## **9 COMPUTER SOFTWARE**

All analyses will be performed by Theorem Clinical Research using Version 9.2 or later of SAS® software. All summary tables and data listings will be prepared utilizing SAS® software.

The standard operating procedures (SOPs) of Theorem Clinical Research will be followed in the creation and quality control of all data displays and analyses.

## 11 APPENDICES

### 11.1 APPENDIX 1: VARIABLE DEFINITIONS

- Body mass index (BMI; kg/m^2) is calculated as: weight (kg) / [height (m)], rounded to one decimal place.
- Body surface area (BSA; m^2) is calculated using Mosteller formula as:  
$$BSA = (H * W / 3600)^{0.5}$$
  
Where W = weight in kg and H= height in cm

- Weight will be displayed in kilograms (kg), height will be displayed in centimeters (cm), and temperature will be displayed in Celsius (C).
- Weights, heights, or temperatures recorded in alternate units will be converted to the units being displayed using standard conversion formulas.
- Length of Operative Time (mins) = time of chest closure –time of chest incision
- Length of Initial Hospital Stay (Days) = Date of discharge following device implantation – date of implant + 1
- For days on or after the device is implanted:  
Relative Study Day (Rel Day) = Date of Assessment – Date of implant + 1.

For days before the device is implanted:

Relative Study Day (Rel Day) = Date of Assessment – Date of implant.

- Days survived = Date of death/date of event for censoring – Date of implant + 1
  - Days of hospitalization = Date of discharge from hospital – Date of admission + 1
  - Cumulative days of hospitalization after initial hospitalization is the sum of the length of hospital stays after initial hospitalization.
  - Days to explant = Date of explant – Date of initial implant + 1
  - Days to transplant = Date of transplant – Date of initial implant + 1
  - Change from baseline (CFB) = Visit value – Screening/Pre-Implant value
- Calculation of adverse event rate per patient-year**
1. Calculate the patient-years contributed by each patient. The time in the study starts at enrollment. The end date would be the last follow up date (end of study), unless the patient has an explant (when the pump is removed, turned off, or exchanged), dies, or is lost to follow-up prior to the end of study. The patient years are calculated as (date of explant or death or last follow up or end of study – date of enrollment + 1)/365.24. When the number of days is negative, the value will be missing for the patient-years.
  2. Sum the patient-years across all patients in the study. Round to 2 decimal places. This is the denominator.
  3. Sum the total number of events for a particular adverse event (prior to exchange). If a patient has patient-years that is missing, the AEs will not be counted for these patients (e.g., patients who have ongoing AEs that are entered into the database, an exchange after the AE but prior to enrollment).

4. The adverse event rate per patient-year = (Sum of the total number of events for the particular adverse event (prior to exchange))/(Sum of the patient-years across all patients in the study).

## 11.2 APPENDIX 2: KCCQ Determination

There are 10 summary scores within the KCCQ, which are calculated as follows:

### Physical Limitation

The Physical Limitation score corresponds to questions 1a through 1f. Responses to questions 1a through 1f should be coded numerically as follows:

- 1 = Extremely Limited
- 2 = Quite a bit Limited
- 3 = Moderately Limited
- 4 = Slightly Limited
- 5 = Not at all Limited
- 6 = Limited for other reasons or did not do the activity

If the responses to questions 1a through 1f are not values 1, 2, 3, 4 or 5 then the response is set to missing. Note that a response of 6 (Limited for other reasons or did not do the activity) is treated as a missing value. If at least three responses to questions 1a-1f are not missing, then the physical limitation score is computed by calculating the mean response and standardizing the result as follows:

$$\text{Physical Limitation} = 100 * (\text{Mean Response} - 1) / 4$$

### Symptom Stability

The Symptom Stability score corresponds to question 2. Responses to question 2 should be coded numerically as follows:

- 1 = Much Worse
- 2 = Slightly Worse
- 3 = Not Changed
- 4 = Slightly Better
- 5 = Much Better
- 6 = I've had no symptoms over the last 2 weeks

If the response is 6 (no symptoms over last 2 weeks) then set the response to 3 (not changed). If question 2 is not missing then the symptom stability score is computed by standardizing the result as follows:

$$\text{Symptom Stability} = 100 * (\text{Response} - 1) / 4$$

### Symptom Frequency

The Symptom Frequency score corresponds to questions 3, 5, 7 and 9. The responses should be coded sequentially (1, 2, 3...) in order of increasing health status as follows:

#### Question 3

- 1 = Every Morning
- 2 = 3 or more times per week, but not every day
- 3 = 1-2 times a week
- 4 = Less than once a week
- 5 = Never over the past 2 weeks

#### Questions 5 and 7

- 1 = All of the time
- 2 = Several times per day
- 3 = At least once a day
- 4 = 3 or more times per week, but not every day
- 5 = 1-2 times per week
- 6 = Less than once a week
- 7 = Never over the past 2 weeks

#### Question 9

- 1 = Every night
- 2 = 3 or more times a week, but not every day
- 3 = 1-2 times a week
- 4 = Less than once a week
- 5 = Never over the past 2 weeks

If three or more responses are missing then symptom frequency cannot be computed and will be missing. Otherwise, the symptom frequency is computed by calculating the mean of the standardized responses and multiplying by 100 as follows:

$$\text{Symptom Frequency} = 100 * \text{Mean}((Q3 - 1)/4, (Q5 - 1)/6, (Q7 - 1)/6, (Q9 - 1)/4)$$

### Symptom Burden

The Symptom Burden score corresponds to questions 4, 6 and 8. The responses should be coded numerically as follows:

- 1 = Extremely Bothersome
- 2 = Quite a bit Bothersome
- 3 = Moderately Bothersome

4 = Slightly Bothersome

5 = Not at all Bothersome

6 = I've had no swelling (fatigue, shortness of breath)

If a response is 6 (none) then set the response to 5 (not at all). If at least one response is present then symptom burden score is computed by calculating the mean response and standardizing the result as follows:

$$\text{Symptom Burden} = 100 * (\text{Mean Response} - 1) / 4$$

#### Total Symptom

The Total Symptom score is calculated as the mean of the symptom frequency score and symptom burden score.

#### Self-Efficacy

The Self-Efficacy score corresponds to questions 10 and 11. The responses should be coded numerically as follows:

##### Question 10:

1 = Not at all sure

2 = Not very sure

3 = Somewhat sure

4 = Mostly sure

5 = Completely sure

##### Question 11:

1 = Do not understand at all

2 = Do not understand very well

3 = Somewhat understand

4 = Mostly understand

5 = Completely understand

If at least one question response is present then the self-efficacy score may be computed by standardizing the mean response as follows:

$$\text{Self-Efficacy} = 100 * (\text{Mean Response} - 1) / 4$$

#### Quality of Life

The Quality of Life score corresponds to questions 12, 13 and 14. The responses should be coded numerically as follows:

## Question 12:

- 1 = It has extremely limited my enjoyment of life
- 2 = It has limited my enjoyment of life quite a bit
- 3 = It has moderately limited my enjoyment of life
- 4 = It has slightly limited my enjoyment of life
- 5 = It has not limited my enjoyment of life at all

## Question 13:

- 1 = Not at all satisfied
- 2 = Mostly dissatisfied
- 3 = Somewhat satisfied
- 4 = Mostly satisfied
- 5 = Completely satisfied

## Question 14:

- 1 = I felt that way all of the time
- 2 = I felt that way most of the time
- 3 = I have occasionally felt that way
- 4 = I have rarely felt that way
- 5 = I have never felt that way

If at least one question response is present then the quality of life score may be computed by standardizing the mean response as follows:

$$\text{Quality of Life} = 100 * (\text{Mean Response} - 1) / 4$$

Social Limitation

The Social Limitation score corresponds to questions 15a through 15d. These responses should be coded numerically as follows:

- 1 = Severely Limited
- 2 = Limited Quite a bit
- 3 = Moderately Limited
- 4 = Slightly Limited
- 5 = Did Not Limit at All
- 6 = Does not apply or did not do for other reasons

If the responses to questions 15a through 15d are not values 1, 2, 3, 4 or 5 then the response is set to missing. Note that a response of 6 is treated as a missing value. If at least two question responses are present then the social limitation score may be computed by standardizing the mean response as follows:

$$\text{Social Limitation} = 100 * (\text{Mean Response} - 1) / 4$$

### Clinical Summary Score

The Clinical Summary score is calculated as the mean of the physical limitation score and total symptom score.

### Overall Summary Score

The Overall Summary score is calculated as the mean of the physical limitation score, total symptom score, quality of life score and social limitation score.

## 11.3 APPENDIX 3: EuroQol 5D-5L Determination

The EQ-5D™ has two parts. The first part is a descriptive system that classifies respondents into one of 243 distinct health states. The descriptive system consists of the following five dimensions:

1. Mobility (MO).
2. Self-care (SC).
3. Usual activities (UA).
4. Pain/discomfort (PD).
5. Anxiety/depression (AD).

Each dimension has five possible levels (i.e., 1 to 5), representing "no problems," "slight problems", "moderate problems", "severe problems", and "unable to/extreme problems" respectively. Respondents are asked to choose one level that reflects their "own health state today" for each of the five dimensions. This health state classifier can describe 3125 unique health states that are often reported as vectors ranging from 11111 (full health) to 55555 (worst health).

The second part is a 20-cm visual analog scale (EQ-VAS) that has endpoints labeled "best imaginable health state" and "worst imaginable health state" anchored at 100 and 0, respectively. Respondents are asked to indicate how they rate their own health by drawing a line from an anchor box to that point on the EQ-VAS which best represents their own health on that day. Hence, the EQ-5D™ produces three types of data for each respondent:

1. A profile indicating the extent of problems on each of the five dimensions represented by a five-digit descriptor (e.g., 11121, 33211)
2. A population preference-health index value based on the descriptive system.
3. A self-reported assessment of health status based on the EQ-VAS.

Missing values should be left blank. The index value will not be calculated when responses are missing for one or more of the dimensions.

## 11.4 APPENDIX 4: STATISTICAL ANALYSIS AND PROGRAMMING DETAILS

Exact binomial confidence intervals:

- *Make sure the outcome variable is coded properly since BINOMIAL option computes the binomial proportion and confidence limits for the first level of the variable. For example, if outcome is coded 'alive vs dead' the output will have test statistics and confidence limits for survival. If the outcome is coded 'death vs survival', then output will have test statistics and confidence limits for the mortality.*
- *Make sure appropriate alpha is specified since the procedure always produces 2sided confidence limits.*
  - *To obtain 1-sided 95% confidence limits, specify alpha=0.10*
  - *To obtain 2-sided 95% confidence limits, specify alpha=0.05*

*The following is example syntax of SAS code to produce the 2-sided 90% exact binomial confidence intervals.*

```
PROC FREQ DATA=sur6;
  WEIGHT n;
  TABLE outcome / BINOMIAL ALPHA=0.10;
  EXACT BINOMIAL;
  OUTPUT OUT out=bio BIN;
Run;
```

*Where n is total number of patients with outcome of alive and total number of patients with outcome of dead at 6 months. Outcome = Alive or Dead*

*For hypothesis of primary endpoint,*

```
Data result; Set
  bio;
  If round(XL_BIN, 0.01) > 0.70 then NI='Pass'; else NI='Fail';
Run;
```

*For hypothesis of secondary endpoint,*

```
Data result; Set
  bio;
  If round(XL_BIN, 0.01) > 0.52.5 then NI='Pass'; else
NI='Fail';
Run;
```

Kaplan-Meier (KM) Survival Analysis:

*The SAS procedure LIFETEST will be used for Kaplan-Meier survival analysis.*

- *Censored = 1 for all patients survived, patients with transplant or explant, patients discontinued without event of death or lost to follow-up*
- *Censored = 0 for all patients died.*

*The following code will be used:*

```
ods listing close;  
ods output CensoredSummary=censor quartiles = _qt;  
PROC LIFETEST DATA = surv TIMELIM=n;  
TIME surdays*censored(1); run; ods  
listing; ods output close;
```

- *Option TIMELIM is the maximum observation period*
- *surdays= number of days survived post implant*
- *dataset censor contains number of patients censored for this analysis*
- *data \_qt contains KM 25% quartile, median, and 75% quartile estimates of time to death*

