## 12.0 STATISTICAL CONSIDERATIONS

### 12.1 General Statistical Considerations

All data collected in this study will be documented using summary tables and subject data listings. For categorical variables, frequencies and percentages will be presented. For continuous variables, descriptive statistics (n, mean, standard deviation, median, minimum and maximum) will be presented.

Demographic data, including gender, race, age and body surface area (BSA), and baseline assessments (e.g., chronic heart failure (CHF) etiology, cardiovascular history, current hospital admission) will be summarized using frequencies and percentages, or descriptive statistics, as applicable.

Survival will be calculated as actual survival and as estimated survival using the Kaplan-Meier product limit estimate.

Subjects not eligible for endpoint analysis include lost to follow-up and withdrawals prior to endpoint. Subject ineligibility is unexpected, and this protocol addresses it with a planned occurrence rate well under 5%. Transplants, explants for recovery and exchanges (to a device other than the MVAD pump) prior to endpoint will be eligible for endpoint analysis with survival status identified at the time of the procedure. Survival failure is associated with events (death) on the MVAD pump. Endpoint analyses will be performed at 6 months and 24 months.

Any deviations from the planned statistical analyses will be reported with proper justification as a protocol deviation.

Patient-years and follow-up time are based on database-driven known time on MVAD pump support (including post-exchange time). If a subject is on MVAD pump support at last known follow-up and a later date of death exists, the date of death must be considered the last follow-up for that subject. The subject is known to be alive and assumed to be on MVAD pump support up to the date of death.

Statistical analysis will be performed using SAS version 9.1 or higher.

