#### **4.5 Determination of Sample Size**

The primary endpoint is survival at 6 months presented as a simple proportion (binomial rate). The survival rate at 6 months is estimated to be 85%, based on HeartWare's experience with the HVAD. This estimated rate will be compared to a performance goal (70%). A sample of 57 subjects is required to satisfy a one-sided significance level of 0.05 and a power greater than 80% (the lower bound of a one-sided 95% exact binomial confidence interval must exceed 70% for success). Three additional subjects (for a total of 60) will be implanted with the MVAD® pump to address for possible attrition due to lost to follow-up or withdrawal.

The first secondary endpoint is survival at 24 months presented as a simple proportion (binomial rate). The survival rate at 24 months is estimated to be 70%, based on HeartWare's experience with the HVAD. This estimated rate will be compared to a performance goal (52.5%). A sample of 57 subjects is required to satisfy a one-sided significance level of 0.05 and a power greater than 80% (the lower bound of an exact binomial confidence interval must exceed 52.5% for success). Three additional subjects (for a total of 60) will be implanted with the MVAD® pump to address for possible attrition due to lost to follow-up or withdrawal.

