#### **5.2 Changes from the Analyses Planned in the Protocol/CIP**

Due to the early stop of the protocol, fewer than 15 subjects were enrolled. As such, summary statistics are of little use. Therefore, case studies for each subject enrolled and followed will be presented and summary statistics are no longer planned.

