## 7 STATISTICAL METHODS

### 7.1 General Methodology

All analysis will be performed using SAS® Version 9.2 or higher. Data will be summarized using descriptive statistics (number of patients [N], mean, standard deviation [SD], median, minimum, and maximum) for continuous variables and using frequency and percentage for discrete variables.

The primary and secondary efficacy analyses for survival (simple proportion) will be based on the lower bound of the one-sided 95% exact binomial confidence interval exceeding the performance goal. No other hypothesis testing will be performed.

Patient listings of all data from the case report forms (CRFs) as well as any derived variables will be presented.

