### 8.7.1 Analysis of Primary Efficacy Variable – Overall Survival at 6 Months

The primary endpoint is survival at 6 months presented as a simple proportion (subjects alive on the MVAD® pump divided by endpoint eligible subjects). Transplants, explants for recovery and exchanges (to a device other than the MVAD® Pump) prior to 6 month follow-up will be eligible for endpoint analysis (with survival status identified at the time of the procedure). Trial failure is associated with events (death) on the MVAD® Pump. The survival incidence at 6 months is estimated to be 85%, based on HeartWare's experience with the HVAD. This estimate will be compared to a performance goal (PG1). The null and alternative hypotheses are provided below:

$$H_0: \pi_{MVAD1} \leq PG_1$$

$$H_A: \pi_{MVAD1} > PG_1$$

$\pi_{MVAD1}$  is the estimated proportion of survival in the treatment group. The performance goal at 6 months is 70%. Success is achieved if the lower bound of the one-sided 95% exact binomial confidence interval exceeds the performance goal.

A summary table will include number of patients alive and number of patients dead by study day 183 (the lower bound of the 6 month visit), the proportion for overall survival at 6 months, and the associated lower and the upper 90% exact binominal confidence intervals.

Sensitivity analysis will be performed to assess the impact of the missing data (See Section 8.7.5.1).

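### SAP Appendix 4 rounds the lower bound to two decimals before testing it against 70%, contradicting the stated success rule: at n = 57, 46 survivors succeed by the text and fail by the code

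*SAP*

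**What the plan says.** SAP 8.7.1 gives the primary rule: "Success is achieved if the lower bound of the one-sided 95% exact binomial confidence interval exceeds the performance goal". SAP 7.1 bases both survival tests on the "lower bound of the one-sided 95% exact binomial confidence interval exceeding the performance goal". Protocol 12.3 has the same rule, and SAP 4.5 uses it to justify the sample size: "A sample of 57 subjects is required to satisfy a one-sided significance level of 0.05 and a power greater than 80" percent. None of these places mentions rounding.

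The decision step for the primary endpoint in SAP 11.4 (Appendix 4) is: "If round(XL_BIN, 0.01) > 0.70 then NI='Pass'; else NI='Fail". The step for 24-month survival is: "If round(XL_BIN, 0.01) > 0.52.5 then NI='Pass'; else".

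SAP version 2.0, section 5.2, reports that the study stopped early with fewer than 15 subjects enrolled, and that "case studies for each subject enrolled and followed will be presented and summary statistics are no longer planned". It does not mention the success tests in 7.1 and 8.7 or the Appendix 4 code.

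**The concern.** The text compares the bound itself with 0.70. The code compares the bound after rounding it to the nearest 0.01. Under a strict inequality, any bound above 0.70 but below 0.705 rounds to 0.70 and is labelled a failure. The plan therefore holds two thresholds for one primary endpoint, and nothing explains or authorises the higher one. A programmer following the appendix could report a failure that the plan's own rule calls a success. With both rules in the plan, the choice between them could also be made after the data are seen.

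The secondary step has a further defect: its threshold is printed with two decimal points and is not a valid number.

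**Working it through.** **Inputs.** From SAP 4.5: n = 57, with 60 implanted to allow for attrition; performance goal 0.70; expected survival 0.85; one-sided level 0.05; power above 80%. From SAP 11.4: the 90% two-sided exact interval (alpha = 0.10), whose lower limit is the one-sided 95% bound, rounded to 0.01 and compared strictly with 0.70.

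**Formula.** For x survivors of n, the exact (Clopper-Pearson) bound L(x, n) is the 5th percentile of a Beta(x, n − x + 1) distribution. With cutoff c, size is P(X ≥ c) at p = 0.70 and power is P(X ≥ c) at p = 0.85, where X is Binomial(n, p).

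**Step 1: the plan's own figure (unrounded rule, n = 57).**
- L(45, 57) = 0.6813, L(46, 57) = 0.7008 and L(47, 57) = 0.7206, so the cutoff is 46.
- Size = 0.0486 and power = 0.8621. The stated claim of more than 80% is reproduced.

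**Step 2: the coded rule (n = 57).**
- 0.7008 rounds to 0.70, and 0.70 > 0.70 is false, so 46 of 57 fails.
- 0.7206 rounds to 0.72 and passes, so the cutoff is 47.
- Size = 0.0241 and power = 0.7717.
- The rules differ only at exactly 46 survivors, which has probability 0.8621 − 0.7717 = 0.0904 when survival is 85%.

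**Step 3: neighbouring sample sizes.**

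| n | Cutoff, text (bound) | Cutoff, code | Power, text | Power, code |
|---|---|---|---|---|
| 53 | 43 (0.701) | 44 | 83.8% | 73.4% |
| 54 | 44 (0.706) | 44 | 82.2% | 82.2% |
| 55 | 45 (0.711) | 45 | 80.6% | 80.6% |
| 56 | 46 (0.716) | 46 | 78.9% | 78.9% |
| 57 | 46 (0.701) | 47 | 86.2% | 77.2% |
| 58 | 47 (0.706) | 47 | 84.9% | 84.9% |
| 59 | 48 (0.710) | 48 | 83.4% | 83.4% |
| 60 | 49 (0.715) | 49 | 81.9% | 81.9% |

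**Step 4: sizes possible after the early stop (n < 15).** When all survive, the bound is 0.05^(1/n). For n = 8 it is 0.6877, so no result can pass at n ≤ 8. For n = 9 it is 0.7169. From n = 9 to 13 both rules pass only if all survive (for example, 12 of 13 gives 0.6837 and 13 of 13 gives 0.7942). At n = 14 they differ: 13 of 14 gives 0.7033, a pass by the text and a fail by the code.

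**Step 5: the secondary endpoint.** Reading the printed threshold as 0.525, rounding does no harm, because 0.525 is itself a rounding midpoint: a bound above it rounds to at least 0.53 and a bound below it to at most 0.52. At n = 57 the cutoff is 37 (bound 0.5322) either way, and no cutoff changes for any n from 5 to 70.

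**The case against.** The strongest reply is that events have overtaken the point. Version 2.0 of the SAP replaces summary statistics with case studies. The pass/fail label is computed from the pooled proportion and its bound, so without them the code has nothing to act on. This largely stands as to consequence. It does not settle the text: section 5.2 does not name the tests or the code as withdrawn, and the revision made for the final analysis left both in place.

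Second, the rules agree where the trial was expected to land. Protocol 12.1 says of ineligibility that "this protocol addresses it with a planned occurrence rate well under 5" percent. Five percent of 60 is 3, so fewer than 3 lost means 58 to 60 evaluable. This stands, but 57 is the size on which the documents rest their power statement.

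Third, among the sizes still possible only n = 14 matters. If enrolled has its SAP 8.3.1 meaning of having signed consent, 14 evaluable subjects would require 14 enrolled and none lost before anesthesia or the endpoint. This also stands.

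Fourth, the code may be only illustrative. The appendix introduces its binomial syntax as an example, whereas its Kaplan-Meier code is presented as the code to be used. The example label, however, is attached to the step that produces the intervals. The decision step has its own heading and is the only place where success is coded. Quality control might catch the error, since the secondary line could not run as printed, but that does not reconcile the two rules.

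Finally, the sample-size claim itself is not wrong: SAP 4.5 ties it to the unrounded rule, under which it reproduces.

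**Conclusion.** The concern holds and is minor. The appendix code contradicts the success rule given in the protocol and three times in the SAP text. At n = 57 it raises the required survivors from 46 to 47, lowers power from 86.2% to 77.2% and lowers exact size from 4.9% to 2.4%. It is conservative, changes no decision at n = 58 to 60, and has no effect on the secondary endpoint once the threshold is read as 0.525. Given SAP 5.2, the practical effect on this trial is probably nil.

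The power figures assume the plan's 85% survival. They treat the rounded bound as equal to 0.70 when it rounds to that value, with halves rounded up.

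**What to change.** Test the unrounded bound in both decision steps (XL_BIN > 0.70 and XL_BIN > 0.525) and round only for display. This also repairs the invalid secondary threshold. Exact size at n = 57 moves from 2.4% to 4.9%, still within the stated 5%.

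Alternatively, if the tests are no longer intended, say in SAP 5.2 that the tests in 7.1 and 8.7 are withdrawn, and mark the Appendix 4 decision code accordingly.

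The cost is two lines of appendix code or a short statement of withdrawal. Neither route changes the design, the sample size or data collection.

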### ***8.7.2 Analysis of Secondary Efficacy Variable – Overall Survival at 24 Months***

The first secondary endpoint is survival at 24 months presented as a simple proportion (defined like the primary endpoint). The survival incidence at 24 months is estimated to be 70%, based on HeartWare's experience with the HVAD. This estimate will be compared to a performance goal (PG2). The null and alternative hypotheses are provided below:

$$H_0: \pi_{MVAD2} \leq PG_2$$

$$H_A: \pi_{MVAD2} > PG_2$$

$\pi_{MVAD2}$  is the estimated proportion of survival in the treatment group. The performance goal at 24 months is 52.5%. Success is achieved if the lower bound of the one-sided 95% exact binomial confidence interval exceeds the performance goal.

A summary table will include the number of patients alive and number of patients dead by study day 730 (the lower bound of the 24 month visit), proportion of overall survival at 24 months and the associated lower and the upper 90% exact binominal confidence intervals.

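### SAP Appendix 4: the decision step for 24-month survival has an invalid threshold and reads only 6-month counts, so it does not implement the rule in SAP 8.7.2 and protocol 12.4

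*SAP*

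**What the plan says.** The rule in the text is clear. SAP 8.7.2 states "The performance goal at 24 months is 52.5" per cent and defines success as the exact one-sided 95% binomial lower bound lying above that goal. Protocol 12.4 sets the same goal and criterion. SAP 6.4.2 takes survival status at Relative Study Day 730.

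Appendix 4 (SAP 11.4) then gives code:

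- One frequency step, introduced with "The following is example syntax of SAS code to produce the 2-sided 90% exact binomial confidence intervals". It begins "PROC FREQ DATA=sur6" and writes its output to `bio`. The counts are explained by "Where n is total number of patients with outcome of alive and total number of patients with outcome of dead at 6 months".
- A decision step for the primary endpoint, which reads `bio`: "If round(XL_BIN, 0.01) > 0.70 then NI='Pass'; else NI='Fail".
- A decision step for the secondary endpoint, which also reads `bio`: "If round(XL_BIN, 0.01) > 0.52.5 then NI='Pass".

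Both decision steps write to a data set called `result`. No 24-month data set and no second frequency step are printed. SAP 5.2 (version 2.0) reports that fewer than 15 subjects were enrolled after the early stop and replaces summary statistics with case studies. Section 8.7.2 and Appendix 4 remain in that version and are not marked as withdrawn.

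**The concern.** The 24-month comparison is one of only two formal tests in the plan (SAP 7.1), and its data are meant to support long-term use labeling (protocol 6.1, SAP 3). The code printed for it has two faults of different kinds.

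The threshold `0.52.5` has two decimal points and looks like a mixture of 0.525 and 52.5. This fault announces itself: the step will not compile, and someone will correct it.

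The input fault is silent. Once the number reads 0.525, the step runs cleanly, but the bound it examines is the one for 6-month survival. The 24-month verdict would then depend on deaths in the first six months only, measured against a goal set for two years.

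**Working it through.** **Inputs.** Goals 70% (6 months) and 52.5% (24 months); planning survival 85% and 70%; one-sided 5% level; 57 evaluable subjects with power above 80% (SAP 4.5, protocol 12.3 and 12.4). Appendix 4 obtains the one-sided bound as follows: "To obtain 1-sided 95% confidence limits, specify alpha=0.10".

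**Formulas.** For x alive out of n, the exact (Clopper-Pearson) one-sided 95% lower bound is L(x, n) = the 5th percentile of Beta(x, n − x + 1). The critical count r is the smallest x with L(x, n) above the goal. The pass probability at true survival p is P(X ≥ r), with X ~ Binomial(n, p).

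**The plan's own figure first.** At n = 57:

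| Endpoint | r | L(r) | L(r − 1) | Level at the goal | Power |
|---|---|---|---|---|---|
| 24 months, goal 52.5%, planning 70% | 37 | 0.5322 | 0.5143 | 3.97% | 83.7% |
| 6 months, goal 70%, planning 85% | 46 | 0.7008 | 0.6813 | 4.86% | 86.2% |

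The stated sample size and power are reproduced, so the prose rule and the design agree.

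**The step as printed.** `0.52.5` is not a valid numeric constant. The step yields no verdict.

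**The step with only the number corrected to 0.525.** It passes when at least 37 of 57 are alive at 6 months. Its pass probability depends only on 6-month survival:

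| True 6-month survival | Coded 24-month pass | Stated rule, if true 24-month survival is 52.5% |
|---|---|---|
| 70% | 83.7% | 4.0% |
| 75% | 96.8% | 4.0% |
| 80% | 99.8% | 4.0% |
| 85% (planning value) | 99.996% | 4.0% |

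Example: 46 of 57 alive at 6 months (L = 0.7008) and 30 of 57 alive at 24 months (30/57 = 52.6%, L = 0.4098). The stated rule gives Fail at 24 months; the half-repaired code gives Pass.

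**Against the 6-month verdict.** Under the unrounded prose rule the primary needs 46 alive, and the half-repaired secondary step needs 37. Every 6-month count from 37 to 45 (L from 0.532 to 0.681) therefore fails the primary and passes the coded secondary. The probability of a count in that range is 79%, 77%, 47% and 14% at 6-month survival of 70%, 75%, 80% and 85%.

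**At the reduced size.** With n = 14, the largest number consistent with SAP 5.2, r = 11 (L = 0.534). The half-repaired code passes 85.3% of the time at 6-month survival of 85%. The stated rule passes 4.3% of the time at 24-month survival of 52.5%.

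**Rounding.** For every n from 5 to 60, rounding the bound to two decimals changes no verdict against 0.525, so these results do not come from the rounding. In the primary step it does matter at n = 57: 0.7008 rounds to 0.70, which does not exceed 0.70. That is a separate point.

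**The case against.** The case for leaving this alone is substantial. The frequency step is offered as an example, while the Kaplan-Meier block in the same appendix is introduced as the code that will be used, so the SAP itself separates illustration from instruction. The prose is right wherever it governs. SAP 8.7.2 also asks for a table of patients alive and dead by Day 730 with exact limits, which cannot be made from 6-month counts, so a programmer who follows it must repeat the step on 24-month data. SAP 9 places displays and analyses under quality-control procedures. Finally, SAP 5.2 means that the test is no longer a planned summary.

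All of that stands, and it limits the practical weight. It does not make the printed step correct. The decision steps are set out by endpoint, and nothing beside the secondary one says that `bio` must be rebuilt from Day 730 data.

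A reader might infer two stronger things that the documents do not support:

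- **That the coded 24-month verdict simply repeats the 6-month verdict.** It reuses the 6-month bound but holds it to a lower goal, so the two verdicts differ at 37 to 45 of 57 alive.
- **That a failed secondary step would leave the 6-month verdict in `result` under a 24-month label.** Sharing one data set name is poor practice. But the OUTPUT statement that creates `bio` carries OUT twice and also looks malformed (possibly from the PDF reading). Taken literally, the primary verdict may not exist either. The scenario also rests on software behaviour that the documents do not describe.

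**Conclusion.** The point holds as a defect in the printed code, not in the chosen analysis. The Appendix 4 step for the 24-month endpoint cannot run as printed. With only its number corrected, it would judge 24-month survival on 6-month data. At n = 57 the half-repaired step would pass 83.7% to 99.996% of the time for 6-month survival of 70% to 85%, against 4.0% for the stated rule when true 24-month survival sits at the goal.

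These figures assume 57 evaluable subjects, independent binomial outcomes, and a programmer who corrects the threshold but not the input. They show what the code would do if used in that state; they do not predict what was done. Since the trial stopped with fewer than 15 subjects and summary statistics are no longer planned, the effect on this trial's reporting is small. It is still worth correcting: the step carries the threshold and input for one of two formal hypotheses, and version 2.0 leaves it in place without marking it withdrawn.

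**What to change.** Either of two changes to Appendix 4 settles it.

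1. **Correct the code.** Add a second frequency step on Day 730 outcomes as defined in SAP 6.4.2 (for example `sur24`, output to `bio24`), and remove the duplicated OUT from the OUTPUT statement. In the secondary decision step, read `bio24`, compare the unrounded `XL_BIN` with 0.525, and write to its own data set (for example `result24`).
2. **Retire the code.** State that the Appendix 4 decision code does not apply, given SAP 5.2.

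The first costs a few lines of appendix code and the second one sentence. Neither needs new data, subjects or procedures. Compared with the half-repaired code, a 24-month Pass becomes harder to obtain, which is what SAP 8.7.2 intends.
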